Chronic graft-versus-host-disease (GVHD) is a major complication of allogeneic hematopoietic cell transplant that impairs quality of life, and is associated with significant morbidity and mortality. Management of chronic GVHD with prednisone is associated with an overall response rate of approximately 60%, and a complete response rate of approximately 30% but sclerotic features do not respond as well. Based on the biology of chronic GVHD and available preliminary evidence, we hypothesize that ruxolitinib will be effective in the management of sclerotic chronic GVHD. The study is an open label, phase II multicenter trial designed to evaluate the efficacy of ruxolitinib as a salvage treatment for subjects with sclerotic GVHD (sclerosis or fasciitis). The primary objective is to determine the proportion of subjects with response rate (complete and partial responses) in skin and/or joint, as determined by 2014 NIH consensus criteria, at 6 months of therapy with ruxolitinib. Eligibility criteria includes adult subjects with chronic GVHD and skin, joint and/or fascia sclerosis, who have received systemic corticosteroids for >12 months and at least one additional line of therapy OR systemic corticosteroids and at least two additional lines of therapy for chronic GVHD. A sample size of 47 subjects dosed (42 evaluable subjects and estimated 10% dropout) will allow an α of 0.044 and a power of 84% to test the null hypothesis response rate of 25% compared to an alternative of 45%. Subjects will receive ruxolitinib for 6 months for the treatment of sclerotic chronic GVHD. Subjects will be evaluated for GVHD status as well as non-relapse mortality, relapse of underlying malignancy and quality of life/functional status. Plasma cytokine levels and T/NK cell subset in peripheral blood will be measured at various time points. The response rate will be reported as a proportion and 95% exact confidence interval. If positive, the trial results will support other ongoing studies to establish the role of ruxolitinib in chronic GVHD in general and specifically in sclerotic chronic GVHD.

Study Schema

Patients with chronic graft-versus-host-disease and skin, joint and/or fascia sclerosis, who have received systemic corticosteroids for >12 months and at least one additional line of therapy OR systemic corticosteroids and at least two additional lines of therapy

Informed consent and registration

Ruxolitinib therapy for 6 months

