5.6 Criteria for Discontinuation of the Study Drug and Removal from Study

Subjects will discontinue the study drug for any of the following reasons:

- Progression of GVHD resulting in initiation of a new systemic immunosuppressive agent (also see Section 5.1.1)
- Development of an adverse reaction that necessitates discontinuation of the study drug, including any unresolved serious adverse event. Please see section 5.2 for further details.
- Development of a serious systemic allergic response or severe degree of intolerance to the study medication.
- Development of intercurrent medical problems that would make continued protocol therapy detrimental to the subject's safety.
- The subject chooses to discontinue treatment.

Subjects who stop study medication for GVHD progression or relapse of underlying malignancy will stop research visits except for the safety follow-up visit. Data may continue to be collected via chart review.

Subjects will be removed from the study (**study withdrawal**) for any of the following reasons:

- If at any time the requirements of this protocol are detrimental to the subject's wellbeing, the subject will be removed from the study. In this event, the reason(s) for withdrawal will be documented.
- The subject requests removal from the study.

The reason(s) for **study withdrawal** will be documented and no further information may be collected on the subject. The reason(s) for stopping study medication will be documented in the UNMC IRB # 333-18, Protocol Version 1.6 dated 25Jan2021

case report form. If available, the following information will be recorded in the case report form: GVHD status, date of relapse of underlying malignancy, date of death, cause of death, and autopsy report. Subjects who stop the study drug but do not withdraw from the study may remain in the study.

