10.1 Study Design and Sample Size Description

The study is an open label, phase II, multicenter trial designed to evaluate ruxolitinib as a salvage treatment for subjects with sclerotic GVHD (sclerosis or fasciitis).

If a subject receives one dose of ruxolitinib then the subject will be included in the safety analysis set.

The full analysis set will include all subjects that are evaluable at 6 months as well as subjects who are considered a treatment failure (including deaths) prior to 6 months. Subjects who drop out of the study prior to 6 months for reasons unrelated to treatment will be excluded from the full analysis set.

The primary endpoint is complete and partial responses in skin and/or joint, as determined by 2014 NIH Criteria (1) at 6 months from initiation of ruxolitinib without addition of any other systemic chronic GVHD treatment, relapse of the underlying disease, or death. The historical benchmark for overall response for steroid refractory sclerotic chronic GVHD is 25% in a randomized phase II trial by Arai et al., comparing imatinib and rituximab (15). In the trial by Arai et al., a significant clinical response was defined as “2 or more point improvement on the Vienna Skin Score without worsening elsewhere or at least a 1-point improvement in the 4-level P-ROM scale or a 2-point improvement in the 7-level scale without worsening elsewhere.” The Vienna Skin Score is different from the 2014 NIH criteria (1) for responses in skin and/or joint. According to the 2014 NIH guidelines (1), “because the NIH 0 to 3 Skin Score is now recommended for response assessment, even substantial improvement in sclerotic features will not be considered responses unless the NIH Skin Score improves.” For this reason, for the purpose of the stopping rules, responses will include complete and partial responses in skin and/or joint, at least a 2-point improvement on 0-10 semiquantitative scale for capturing clinician-perceived severity of sclerosis, or clinically significant improvement (improvement by ≥ 6 point) on the skin subscale of the Lee symptom scale, consistent with the recommendations of the 2014 NIH Criteria (1). Additionally, improvement in percentage of BSA involved with deep sclerosis/fasciitis will also be taken into consideration as a marker of responses.

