A two-stage design is planned to test the null hypothesis that the overall response rate $p \leq 0.250$ versus the alternative that $p \geq 0.450$. The first stage will occur once 18 subjects have completed 6 months of treatment. If only 4 or fewer out of the 18 subjects respond at the end of 6 months of treatment, the trial will be stopped for futility. At stage two, an additional 24 subjects will be enrolled for a combined total of 42 from both stages. If only 15 or fewer respond out of 42 subjects at the end of stage two, then no further investigation is warranted. If 16 or more respond then further investigation is warranted. This design achieves 84% power with a significance level of 0.044. Retrospective studies (31, 32, 40) have demonstrated that ruxolitinib is well tolerated and effective in patients with steroid-refractory chronic graft-versus-host disease (GVHD) in general and sclerotic GVHD. Therefore, the accrual will not be put on hold for interim analysis.

To meet our statistical endpoints, a sample size of 42 is required; however, to account for dropout rate of approximately 10%, the study will dose 47 subjects.

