10.2.1 Efficacy Endpoints

Primary and secondary objectives

The primary objective of the study is to determine the complete and partial responses in skin and/or joint after 6 months of therapy. The response rate will be reported as a proportion and 95% exact confidence interval. This analysis will be conducted on the full analysis set.

The secondary objective is to determine the overall complete and partial responses after 6 months of therapy. The response rate will be reported as a proportion and 95% exact confidence interval.

Exploratory Objectives

Treatment failure (treatment failure defined as: administration of additional systemic therapy for chronic GVHD, malignancy relapse or mortality) by 6 months from study enrollment.

Time to treatment failure will be defined as study enrollment to failure event. Kaplan-Meier methods will be used to estimate the distribution for time to treatment failure. The failure rate at 6 months will be estimated from the Kaplan-Meier curve, and the rate and 95% confidence interval will be reported.

Time to non-relapse mortality will be computed as study enrollment to non-relapse death. Cumulative incidence methods will be used to estimate the distribution with relapses and relapse related deaths as competing events. The rate at 6 months will be estimated from the curve along with 95% confidence intervals.

For subjects treated on the extension study, the response rate at 12 months will be reported as a proportion and 95% exact confidence interval.

For subjects on steroids at baseline, we will explore the change in dose of steroids at 6 months. We will calculate the average percent change in dose for each subject along with a 95% CI. We will also determine the number and proportion of subjects that had a dose reduction greater than 50% as well as an exact 95% confidence interval.

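### The primary response rate leaves out dosed subjects whose dropout is judged unrelated to treatment, and no all-dosed response rate is planned as a check

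*Combined protocol and SAP*

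**What the plan says.** Section 10.1 defines two sets. Anyone who receives one dose of ruxolitinib is in the safety analysis set. The full analysis set holds subjects evaluable at 6 months plus those who failed treatment or died earlier, and then: "Subjects who drop out of the study prior to 6 months for reasons unrelated to treatment will be excluded from the full analysis set". Section 10.2.1 says of the primary response rate: "This analysis will be conducted on the full analysis set". Section 10.2.3 uses the safety set for safety only.

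The failure definition in sections 1.3 and 10.2.1 is narrow: "treatment failure defined as: administration of additional systemic therapy for chronic GVHD, malignancy relapse or mortality". Section 5.1.1 adds that prednisone above the enrollment dose counts as new systemic treatment.

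Section 5.6 lists as one ground for study withdrawal: "The subject requests removal from the study". It says that after withdrawal nothing further may be collected on the subject, although it also lists items, GVHD status among them, to be recorded if available.

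On numbers, 42 evaluable subjects are needed, and "to account for dropout rate of approximately 10%, the study will dose 47 subjects". The go rule needs at least 5 responders of 18 at stage 1 and at least 16 of 42 at the end, against a null rate of 25%.

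**The concern.** With no control arm, one proportion is compared with a fixed 25%, so the choice of denominator feeds straight into the go decision. The exclusion acts after dosing and depends on the reason for leaving. The documents do not say what makes a reason unrelated to treatment, who decides, or when. Section 10.1 also says: "The study is an open label, phase II, multicenter trial". Treatment and clinical course are therefore known when the reason is recorded.

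A withdrawal at the subject's request fits neither category clearly. The Introduction describes responses in sclerotic disease as slow, so a subject who is not improving may have less reason to stay than one who is. If such a subject leaves before any failure event is recorded, the subject can drop out of the denominator, and a failure soon afterwards may never be seen. The reported rate would then exceed the rate among treated patients, and the go rule would pass more often than planned for a drug no better than the benchmark. No planned analysis would show how much the result depends on these exclusions.

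**Working it through.** **Inputs (sections 10.1 and 10.2.1).** Null rate 0.25; alternative 0.45; stage 1 n = 18, stop at 4 or fewer; final n = 42, go at 16 or more; dropout about 10%; 47 dosed.

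**Formula.** P(go) = sum over x = 5 to 18 of P(X1 = x) × P(X2 ≥ 16 − x), with X1 ~ Bin(18, p) and X2 ~ Bin(24, p).

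**The plan's own figures.**
- Dosed number: 42/0.9 = 46.7, rounded up to 47. Reproduces.
- Power at p = 0.45: 0.8406. Reproduces the stated 84%.
- Alpha at p = 0.25: 0.0397, or 0.0416 if the interim look is ignored. The stated 0.044 does not reproduce. The difference is on the conservative side and does not affect this point.

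**Effect of the exclusion.** Let the true rate among all dosed be 25%, so the expected number of responders among 47 is 0.25 × 47 = 11.75. If k non-responders are excluded, the rate among those kept is 11.75/(47 − k). Put through the same 42-subject rule:

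| Excluded, all non-responders | Rate among those kept | P(go) |
|---|---|---|
| 0 | 25.0% | 0.040 |
| 2 of 47 | 26.1% | 0.057 |
| 3 of 47 | 26.7% | 0.068 |
| 5 of 47 | 28.0% | 0.097 |

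The rows for 2 and 3 are approximate, because 45 or 44 subjects would remain while the rule is written for 42.

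**Exactly 10% dropout, all non-responders.** 0.25/0.9 = 27.8%, P(go) = 0.092. A simulation with accrual fixed at 47 dosed, in which the evaluable number can fall short of 42, gives 0.082.

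**Partly informative dropout at 10%.** If a share s of dropouts are certain non-responders and the rest respond like those kept, the rate among those kept is 0.25/[0.9 + 0.1(1 − s)]. For s = 0, 0.25, 0.50, 0.75 and 1, P(go) is 0.040, 0.049, 0.060, 0.075 and 0.092.

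**One of five excluded would have responded.** (11.75 − 1)/42 = 25.6%, P(go) = 0.048.

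**At the go threshold.** 16/42 = 38.1% (exact 95% CI 23.6 to 54.4%). If five more were dosed and none responded, 16/47 = 34.0% (20.9 to 49.3%). The gap is about 4 points.

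**What happens if the denominator is simply changed to 47 (stage 1 unchanged).**

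| Final cut-off | Alpha at 25% | Power at 45% | Power at 40.5% |
|---|---|---|---|
| 16 of 47 | 0.094 | 0.925 | 0.81 |
| 17 of 47 | 0.054 | 0.893 | 0.74 |
| 18 of 47 | 0.029 | 0.842 | 0.65 |

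The last column is the case where 45% holds among evaluable subjects and 10% of those dosed drop out as non-responders: 0.45 × 0.9 = 40.5%.

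**The case against.** The plan declares an evaluable-subject denominator with a margin for dropout, and the 16-of-42 rule is calibrated to it. Which denominator should lead is partly a matter of preference.

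Several safeguards limit the gap. Deaths and treatment failures stay in as non-responders, so the most evident failures are not lost. Section 5.6 lets subjects who stop the drug remain in the study, and section 5.4 schedules GVHD evaluation at month 6 after early stopping for progression, toxicity or relapse. Sections 5.5.6 and 7.0 call for a GVHD assessment at the safety visit after early treatment withdrawal, though they do not say whether it feeds the primary endpoint. Section 5.1 lets subjects with mixed responses, or progression that needs no new agent, stay on drug to month 6. Reasons for withdrawal must be documented, and section 9.4 provides semi-annual audit. All of this stands and narrows the problem to withdrawals with no recorded failure event.

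Three stronger readings are tempting but not supported:
- A reader might infer that the false-go risk roughly doubles. That needs every excluded subject to be a non-responder, and the documents give no evidence on how informative dropout will be.
- A reader might infer that site staff decide who is excluded. No section says who makes the judgement.
- A reader might call this the only efficacy set. Section 10.2.1 ties it to the primary analysis and names no set for the secondary endpoint or for time to treatment failure.

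**Conclusion.** The point holds as a conditional bias with no planned check on it. The direction is upward whenever excluded subjects respond less often than those kept; if dropout is unrelated to outcome, there is no bias. At a true 25% among dosed subjects and about 10% dropout, the false-go probability lies between 0.040 and about 0.08 to 0.097. The upper end depends on whether accrual is held at 47 and whether exactly five subjects are excluded. If half of the dropout is informative it is 0.060, above the stated 0.044.

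The figures assume independent subjects with a common response rate and the same response definition at both stages. Section 10.1 describes a wider definition for the stopping rules. If that made the interim stop less likely, the figures would move towards the single-stage values: 0.0416 rather than 0.0397 with no bias, and 0.101 rather than 0.097 in the worst case.

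This does not show that the planned set is invalid or that the 16-of-42 rule should be dropped. It shows that the reported rate needs an all-dosed companion.

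**What to change.** Keep the full analysis set and the 16-of-42 rule. In section 10.2.1, pre-specify a supportive response rate with exact 95% confidence interval on all dosed subjects, using the existing safety analysis set. Count any subject without a month-6 response assessment as a non-responder, whatever reason is recorded, and report this rate beside the primary result. It should be descriptive, with no go threshold of its own.

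The cost is a sentence or two of SAP text and one extra proportion from data already held. The downside is a less favourable figure, by up to about 4 points at the go threshold with five exclusions.

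It would also help for section 10.1 to state what makes a dropout unrelated to treatment and who decides.

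If the sponsor prefers all dosed subjects as the primary denominator, the cut-off must be recalibrated. Carrying 16 over to 47 gives an alpha of 0.094, almost the worst case the change is meant to prevent. The amendment should then state the chosen cut-off and its alpha, together with the power loss from non-responding dropouts (0.74 at 17 of 47, 0.65 at 18 of 47, for a 40.5% rate among dosed).

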Steroid intolerant patients have medical complications of steroid therapy (e.g., hyperglycemia, psychosis, osteoporosis), and thus require additional immune-suppressive agents to control GVHD and facilitate taper of prednisone. Multiple immune-suppressive therapies, including pharmacologic agents, monoclonal antibodies, and strategies such as extracorporeal photopheresis have demonstrated moderate activity in this setting, both ameliorating objective chronic GVHD manifestations, as well as facilitating taper of systemic steroids (reviewed in detail in the report of the Consensus Conference on Clinical Practice in Chronic GVHD) (23). Their effectiveness is suboptimal, however, and many patients will require multiple agents to achieve disease control or stabilization. For example, imatinib and rituximab are two commonly utilized therapies for sclerotic chronic GVHD. A randomized phase II trial of imatinib versus rituximab for steroid refractory cutaneous sclerosis conducted at 11 institutions within the Chronic GVHD Consortium demonstrated a significant clinical response rate of 26-27% (15). The overall burden of chronic GVHD despite routine pharmacologic GVHD prophylaxis, limited response to primary and secondary therapies, and the attendant morbidity and mortality all support the need for novel approaches in chronic GVHD treatment.

In August 2017, the Food and Drug Administration approved ibrutinib for management of chronic GVHD after failure of one or more treatments. Ibrutinib is the first therapy to receive FDA approval for the treatment of chronic GVHD. The approval was based on a multicenter single-arm trial of 42 patients with chronic GVHD with inadequate response to corticosteroid (24). The best overall response was 67% at a median follow-up of 13.9 months. A total of 34

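### The 25% null and the 26–27% reported elsewhere for the same benchmark trial need reconciling, and the stated 0.044 should be replaced by the exact error (0.040 at 25%, 0.055–0.074 at 26–27%)

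*Combined protocol and SAP*

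**What the plan says.** The design rests on one external trial, a randomized phase II comparison of imatinib and rituximab (reference 15).

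- Section 10.1 states: "The historical benchmark for overall response for steroid refractory sclerotic chronic GVHD is 25% in a randomized phase II trial". It then tests a response rate of at most 0.250 against one of at least 0.450.
- Section 2.0, under therapy of established chronic GVHD, says that this trial "demonstrated a significant clinical response rate of 26-27" per cent, citing the same reference.
- The decision rule in Section 10.1 has two stages. "The first stage will occur once 18 subjects have completed 6 months of treatment". Four or fewer responders stop the trial for futility. Otherwise 24 more subjects are enrolled, and 16 or more responders out of 42 warrant further investigation.
- Section 10.1 gives the operating characteristics: "This design achieves 84% power with a significance level of 0.044". The protocol summary repeats them, with an alpha of 0.044 and "a power of 84% to test the null hypothesis response rate of 25% compared to an alternative of 45" per cent.
- Section 10.1 also acknowledges that the benchmark trial scored response with the Vienna Skin Score and P-ROM, which differs from the 2014 NIH criteria used here.

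**The concern.** One trial appears with two response rates, and the lower one became the null. Both ends of the range in Section 2.0 lie above 25%, so the discrepancy runs in one direction and makes a go easier to reach. In a single-arm study the null is the only comparator, and the conclusion turns on a single cut-off of 16 out of 42. A reader faced with a result near that cut-off will rely on the quoted significance level to judge how often a drug no better than the benchmark agents would pass. If the benchmark is 26–27%, the quoted level understates that probability. Separately, the quoted level should be reproducible from the stated rule at the stated null, whichever benchmark is right.

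**Working it through.** **Inputs.** All are from Section 10.1 except the second benchmark figure, which is from Section 2.0.

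- Stage 1: n₁ = 18, continue if X₁ ≥ 5.
- Stage 2: 24 further subjects, go if X₁ + X₂ ≥ 16 of 42.
- Null 0.25, alternative 0.45; stated alpha 0.044 and power 84%.
- Benchmark 25% (Section 10.1) or 26–27% (Section 2.0).

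**Formula.** With X₁ ~ Bin(18, p) and X₂ ~ Bin(24, p),

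P(go; p) = Σ from x = 5 to 18 of P(X₁ = x) × P(X₂ ≥ 16 − x).

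**Step 1: the plan's own figures.** At p = 0.25:

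| x | P(X₁ = x) | P(X₂ ≥ 16 − x) | product |
|---|---|---|---|
| 5 | 0.1988 | 0.0213 | 0.00424 |
| 6 | 0.1436 | 0.0547 | 0.00785 |
| 7 | 0.0820 | 0.1213 | 0.00995 |
| 8 | 0.0376 | 0.2338 | 0.00879 |
| 9 | 0.0139 | 0.3926 | 0.00547 |
| 10 | 0.0042 | 0.5778 | 0.00241 |
| 11 or more | | | 0.00097 |
| Sum | | | 0.0397 |

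The stated 0.044 is not reproduced. Other readings do not recover it:

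- Ignoring the futility look gives 0.0416.
- A stage 1 stop at 3 or fewer gives 0.0412, and at 5 or fewer 0.0354.
- A normal approximation with continuity correction gives 0.0374.
- A final cut-off of 17 gives 0.0192.

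At p = 0.45 the formula gives 0.8406, which does reproduce the stated 84%.

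**Step 2: the same rule at the other benchmark figures.**

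| True rate | P(go), two-stage rule | P(go), futility look ignored |
|---|---|---|
| 25% | 0.0397 | 0.0416 |
| 25.5% | 0.0468 | 0.0491 |
| 26% | 0.0549 | 0.0575 |
| 27% | 0.0739 | 0.0774 |
| 45% | 0.8406 | 0.8544 |

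**Step 3: where the thresholds are crossed.** Solving P(go; p) = 0.044 gives p = 0.2531. Solving P(go; p) = 0.05 gives p = 0.2570. Both lie below 26%, the bottom of the range in Section 2.0.

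**Step 4: what a stricter cut-off would do.** With go at 17 or more of 42 and the same first stage, P(go) is 0.0278 at 26%, 0.0392 at 27% and 0.7623 at 45%.

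**The case against.** A null rate is a design choice. The plan names 0.25 and attaches its error rate to that value, and a gap of one to two points fits a benchmark rounded to a convenient figure. The wording also differs: Section 10.1 speaks of overall response and Section 2.0 of significant clinical response. The benchmark was scored differently from the present endpoint, so neither 25% nor 27% is a like-for-like null. It is also imprecise. The protocol does not give that trial's size, but on an assumed 35 to 100 patients an exact 95% interval around 26% would run from roughly 12–43% to 18–36%. A go means only that further investigation is warranted. The response rate will be reported with an exact confidence interval that can be set against any benchmark, and the documents set no 5% ceiling.

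Most of this stands, and it limits the severity and the remedy. It does not remove the point. Section 10.1 goes on to quote that trial's definition of significant clinical response, which suggests that both sections describe one measure. Rounding is plausible but not stated. And the 0.044 fails at the plan's own null, where no argument about the benchmark can help it.

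A reader might infer more than the documents support:

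- That the rule holds its error below 5% only at exactly 25%. It does so up to about 25.7%.
- That the benchmark discrepancy raises the error from 4.4%. The correct starting point is 4.0%; the 0.044 is a separate misstatement, and a conservative one at 25%.
- That 25% is the wrong figure and the null must become 27%. Only the cited source can show which figure is right, and 27% is merely the top of the range given.

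**Conclusion.** The point holds as a should-fix inconsistency. One benchmark trial is given two response rates without explanation, and the lower is the null. At that null the exact error of the go rule is 0.040, not 0.044. At the rates in Section 2.0 it is 0.055 to 0.074, so at 27% a drug no better than the benchmark would pass almost twice as often as at 25% (0.0739 / 0.0397 = 1.86). Power at 45% is 0.84 and is unaffected.

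The figures assume exactly 42 evaluable subjects, independent responses, binding futility at 4 of 18, and one response probability at both looks. Section 10.1 allows a wider set of improvements to count as response for the stopping rules. If that made a futility stop less likely while the final count kept the NIH definition, the error would lie between the two columns of the Step 2 table: at most 0.042 at 25%, 0.057 at 26% and 0.077 at 27%. The conclusion does not change.

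**What to change.** 1. Check both figures against the source and make Sections 2.0 and 10.1 agree. If 25% is a deliberate rounding, say so.
2. Justify the chosen null in Section 10.1 in a sentence or two, noting that the benchmark used a different response definition and so is only an approximate comparator for the NIH-criteria endpoint.
3. Keep the 4/18 and 16/42 rule and the 42 evaluable subjects.
4. In the summary and Section 10.1, replace 0.044 with the exact error at the chosen null (0.040 if 25% is kept), and state beside it the error at 26% and 27% (0.055 and 0.074). Power stays at 84%.

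The cost is wording in the summary and in Sections 2.0 and 10.1, with no extra subjects and no change to conduct. The error quoted at 26–27% will look less favourable than the present text. Moving the final cut-off to 17 of 42 would bring the error at 27% down to 0.039, but power at 45% would fall from 0.84 to 0.76. That trade-off is for the sponsor to weigh, and this point does not require it.

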1.1 Primary Objective

The primary objective of the study is to examine the efficacy of ruxolitinib in subjects with sclerotic chronic graft-versus-host disease (GVHD).

Efficacy will be assessed by:

- Determining the proportion of subjects with complete and partial responses in skin and/or joint, as determined by 2014 NIH Criteria (1), at 6 months of therapy.

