1.2 Secondary Objective

To determine the proportion of subjects with complete or partial responses overall, as determined by 2014 NIH Criteria (1), at 6 months of therapy.

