1.3 Exploratory Objectives

The exploratory objectives are to assess the following:

1. Treatment failure (treatment failure defined as: administration of additional systemic therapy for chronic GVHD, malignancy relapse or mortality) by 6 months from study enrollment
2. Non-relapse mortality by 6 months
3. Change in patient-reported outcomes: skin subscale and summary score of the Lee Chronic GVHD Symptom Scale, and Scleroderma Health Assessment Questionnaire between enrollment and 6 months
4. Response rate in skin/joint and overall at 12 months, for subjects treated on the extension study
5. Proportion who reduce prednisone (or prednisone equivalent) dose by 50% from baseline to 6 months

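### Section 10.1 does not fix which response its 16-of-42 decision counts: the label belongs to the secondary endpoint, and its definition for the stopping rules is wider than the primary endpoint

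*Combined protocol and SAP*

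**What the plan says.** **Endpoints.** The primary objective (1.1) is "Determining the proportion of subjects with complete and partial responses in skin and/or joint" at 6 months. The secondary objective (1.2) is "To determine the proportion of subjects with complete or partial responses overall, as determined by 2014 NIH Criteria". Section 1.3 sets the two terms against each other: "Response rate in skin/joint and overall at 12 months". Section 10.2.1 keeps this usage: "The secondary objective is to determine the overall complete and partial responses after 6 months of therapy".

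**Hypothesis and rules (10.1).** "A two-stage design is planned to test the null hypothesis that the overall response rate" is at most 25%, against an alternative of at least 45%. The futility rule at the first look begins: "If only 4 or fewer out of the 18 subjects respond at the end of 6 months of treatment, the trial will be stopped for". The final rule is: "If only 15 or fewer respond out of 42 subjects at the end of stage two, then no further investigation is warranted"; 16 or more responders support going on. Neither rule names an endpoint.

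**Definition of response (10.1, just before the hypothesis).** After naming the skin/joint primary endpoint, 10.1 says what counts as a response for the stopping rules. Any one of these is enough:

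- an NIH complete or partial response in skin and/or joint;
- a gain of at least 2 points on the clinician's 0-10 rating of sclerosis severity;
- a gain of at least 6 points on the Lee skin subscale.

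A fall in the body surface area with deep sclerosis or fasciitis is also to be considered, with no threshold.

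**Analysis (10.2.1).** Each endpoint gets a proportion and an exact 95% interval. The 16-of-42 rule is attached to neither.

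**The concern.** In a single-arm, open-label trial, 16 of 42 is a test only if it is fixed in advance who counts as a responder. Here the hypothesis carries the secondary endpoint's label, the decision rules name no endpoint, and the one definition offered for the rules is wider than the primary endpoint.

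The wider definition matters in practice. The Lee skin items in Appendix D include abnormal color, rashes and itch as well as thickened skin. A subject could count on that subscale alone, or on the clinician's severity rating alone, with no change in NIH skin score, joint score or P-ROM. If such subjects enter the final count, the trial could meet its go rule while the primary endpoint sits at the rate the design calls uninteresting.

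**Working it through.** **1. Which responses could be counted?**

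| Text | What it points to |
|---|---|
| 10.1 hypothesis: *overall* | By label, the secondary endpoint of 1.2, 1.3 and 10.2.1 |
| 10.1 benchmark: 25% overall response in steroid-refractory sclerotic disease | A sclerosis response, also called *overall* |
| Synopsis: 25% against 45%, without *overall*, after the skin/joint objective | The primary endpoint |
| Synopsis and Section 2: overall response (60%) beside complete response (30%) | *Overall* as complete plus partial |
| 10.1 definition for the stopping rules | Skin/joint response or one of the wider sclerosis and skin measures |

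The label is weak evidence for all-organ response. The two serious candidates are the NIH skin/joint endpoint and the wider definition.

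**2. Does the wider definition reach the final decision?** The text does not say. Read literally, only the 18-subject look stops the trial on response. But 10.1 speaks of rules in the plural. Its reason for widening is that the benchmark trial used a different skin score from NIH, so real improvement in sclerosis may be missed. That reason applies equally to the comparison of 42 subjects with 25%. The mortality rule in 10.4 cannot be what is meant, since it does not use response.

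**3. Reproduce the design.** Inputs from 10.1: 18 subjects at the look, stop at 4 or fewer; 24 more; go at 16 or more of 42. With p the true rate of whatever is counted:

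P(go | p) = sum over x = 5 to 18 of P[Bin(18, p) = x] × P[Bin(24, p) ≥ 16 − x]

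| p | P(stop at 18) | P(go) |
|---|---|---|
| 0.25 | 0.519 | 0.040 |
| 0.30 | 0.333 | 0.157 |
| 0.35 | 0.189 | 0.379 |
| 0.40 | 0.094 | 0.639 |
| 0.45 | 0.041 | 0.841 |

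The stated power of 84% reproduces (0.8406). The stated significance level of 0.044 does not reproduce exactly: the two-stage value is 0.0397, or 0.0416 if the look is ignored. The actual error is below the stated level.

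**4. Size if the wider definition is counted at both stages.** The documents do not say how often an NIH non-responder would qualify on another measure, so the fraction q is assumed. With the NIH skin/joint rate at 25%, the counted rate is p = 0.25 + 0.75q.

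| q (assumed) | p | P(go) |
|---|---|---|
| 0 | 0.2500 | 0.040 |
| 0.05 | 0.2875 | 0.118 |
| 0.10 | 0.3250 | 0.257 |
| 0.15 | 0.3625 | 0.445 |
| 0.20 | 0.4000 | 0.639 |
| 0.25 | 0.4375 | 0.799 |

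**5. Does confining the wider definition to the look upset the design?** No. It counts every primary responder, so the look can only stop the trial less often. P(go) on the primary endpoint then lies between the two-stage value and the value with no look: 0.0397 to 0.0416 at 25%, and 0.8406 to 0.8544 at 45%.

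**The case against.** The strongest defense is that 10.1, read as a whole, already settles the matter. It names the skin/joint primary endpoint, takes the 25% from a sclerosis trial, calls that benchmark an overall response, and then carries both the phrase and the figure into the hypothesis. The synopsis gives the same 25% and 45% straight after the skin/joint objective. On this view *overall* means complete plus partial, and only a wording note is due.

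Much of that stands. A reader might infer from the label that the rule tests all-organ response, so that mouth or eye improvement with unchanged sclerosis could carry the trial. The documents do not support this: no all-organ measure appears in the definition of response for the stopping rules, and the benchmark is a sclerosis figure. Nor can that risk be sized. The higher response rates cited in Section 2 come from initial therapy, from best response on ibrutinib and from a retrospective series, not from 6-month response in pretreated sclerotic disease. A reader might also infer that either endpoint may trigger a go. No such rule exists; the secondary endpoint is only estimated.

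The defense does not close the second gap. The text it relies on is the same text that brings in the wider definition, and nothing there limits that definition to the futility look or ties 16 of 42 to the primary endpoint. It is also fair to say that the figures in step 4 are hypothetical. They show how sensitive the rule is, not what will happen.

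**Conclusion.** The point holds in this form. The tested quantity carries the secondary endpoint's label, though a skin/joint or sclerosis response is almost certainly meant. The real ambiguity is between the primary endpoint and the wider definition, and the plan does not say which one governs the final decision. The go decision can therefore differ from the primary result.

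If only the primary endpoint is counted, the chance of a go at a true rate of 25% is 0.040. If the wider definition is counted at both stages and 5% to 20% of NIH non-responders qualify through it, that chance is 0.118 to 0.639. The 5% to 20% is an assumption, and the calculation also treats subjects as independent with a common rate. This should be corrected, but it is a matter of specification: the sample size, cut-offs and power are sound for whichever endpoint is named.

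**What to change.** - **10.1, hypothesis.** Replace the present label with the proportion of the full analysis set in complete or partial response in skin and/or joint under 6.1, identified as the primary endpoint and keeping 10.1's conditions on added systemic treatment, relapse and death.
- **10.1, decision.** State that the 16-of-42 decision uses that endpoint only.
- **10.1, wider definition.** If it is kept, state that it applies only to the 18-subject futility look.
- **10.2.1.** State that the secondary overall response is estimated with its interval and is not tested against 25%. Keep the word *overall* for that endpoint.

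The cost is a few sentences. No new data are needed, and the sample size and cut-offs do not change. The sponsor gives up the option of citing the wider or the all-organ rate as meeting the go rule.
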